## **2. The entry point and significance of this study**

The entry point of this study is to propose "generative longitudinal prediction": only pre-treatment images are needed to generate high-fidelity post-treatment image predictions, which effectively avoids the clinical dilemma of obtaining real longitudinal follow-up data. This paradigm shift not only solves the problem of longitudinal data scarcity, but also develops a new approach to treatment simulation based on digital twins. Clinicians can intuitively evaluate the possible efficacy of different regimens through the virtual multi-time point images generated by the model before treatment, providing a visual basis for individualized treatment decisions. This study integrates generative AI and dynamic risk models to achieve: 1. From static assessment to dynamic deduction; 2. Survival prediction is moved forward; 3. Individualized optimization of treatment plan. It is expected that we can provide more accurate and individualized treatment decision support for patients with advanced liver cancer without relying on longitudinal data, and ultimately improve the survival prognosis and quality of life.

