## Research content

### 1. Research Objectives

**Main objectives:** 1) To construct a generative image model based on preoperative CT/MRI; 2) the treatment response was evaluated in the training cohort based on the virtual image images generated by the model, including: disease control rate (DCR) and objective response rate (ORR), and compared with the best treatment response images after real treatment; 3) predict the prognosis of patients based on real pre-treatment imaging images (CT/MRI/DSA) and virtual post-treatment images, including progression-free survival (PFS) and overall survival (OS);

**Secondary objectives:** 1) Integrate text information such as patient demographic data, laboratory examination data, and image reports/surgical records to achieve cross-modal fusion and further improve the performance of the model; 2) Adopt machine learning methods based on causal inference to realize the recommendation of diagnosis and treatment plans.

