### **3. Research Methodology**

This study is based on a multicenter retrospective cohort including a prospective test cohort to include patients with unresectable hepatocellular carcinoma who have received TACE in combination with target-immune therapy. The data comes from the clinical diagnosis and treatment records of 8 tertiary hospitals from 2016 to 2025, and strictly follows the preset inclusion standards.

Generative model construction: diffusion model-based treatment response simulator: input data: enhanced CT/MRI images at the patient's baseline, real post-treatment enhanced CT/MRI images and clinical features (Child-Pugh score, AFP level, treatment plan, etc.). Model architecture: The conditional diffusion model was used to dynamically simulate the virtual follow-up images of the best response after treatment with the treatment protocol (TACE embolic agent dose + target immune drug combination) as the generation conditions. Training mechanism: The model is optimized by comparing the differences in deep visual features between the generated images and the real follow-up images to ensure that the generated results conform to the laws of biological evolution. Quantitatively evaluate the visual fidelity of the generated images (FID index <25); The clinical rationality was scored by 3 interventional radiology experts by blind (on a 5-point scale  $\geq$  4 points were considered qualified).

Dynamic survival prediction framework: Capture 256-dimensional semantic feature vectors from the generated virtual images to characterize the dynamic changes of tumor microenvironment. The depth features extracted by the generative model are fused with the patient's clinical variables, and the key predictors are automatically identified through the gated attention mechanism. Survival risk modeling: Construct a Transformer-based time-series survival model to output individualized survival curves and survival probability predictions at key time points (12/24/36 months).

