Treatment decision support systems: causal effects deduction: quantifying the expected survival benefit of different treatment regimens (eg, TACE + lenvatinib + pembrolizumab versus TACE + bevacizumab + atezolizumab) using a counterfactual analysis framework. Generate a heat map of treatment regimen comparisons to visualize simulated tumor regression differences. Decision rule: When the median survival benefit of a regimen is expected to be more than 3 months and the confidence probability is greater than 80%, the system preferentially recommends the regimen.

Model validation strategy: Stratified by study center, randomly assigned to the training set (70%), validation set (30%), and multiple test sets.

Survival prediction assessment: main indicators: C-index evaluation of overall survival prediction

accuracy; Secondary indicators: 12/24/36 months of time dependence on AUC to assess discriminant ability at a specific time point; Calibration analysis: The Brier score quantifies the prediction error, and the calibration curve evaluates the risk prediction consistency. Comparative experimental design: baseline model (clinical variables only); benchmark model + real follow-up images; Datum model + generate model virtual image.

Reproducibility & Ethics: The model code and preprocessing process are published in the public repository (GitHub). The self-service resampling method (1000 times) was used to calculate the 95% confidence interval.

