## **5. The innovation of the project**

This study is a multicenter, retrospective, real-world study of unresectable hepatocellular carcinoma (HCC) undergoing TACE in combination with targeted immunotherapy in the project from January 2016 to June 2025. Baseline imaging data, previous treatments, adverse reactions, clinical outcomes, follow-up imaging data, longitudinal laboratory examination data, etc., were collected to construct a generative model and generate imaging images of the best efficacy after virtual treatment. Combine virtual and real pre-treatment images with other clinical information for accurate prognosis prediction.

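### The model comparison has no clinical plus pre-treatment image model, so it cannot separate what image generation adds to prognosis from what the baseline scan already holds

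*Protocol*

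**What the plan says.** Under the comparative design in section 3 (Research Methodology), the protocol lists three models: "baseline model (clinical variables only); benchmark model + real follow-up images; Datum model + generate model virtual image". The main measure is the "C-index evaluation of overall survival prediction" accuracy.

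On where the virtual image comes from, the section on the entry point and significance of the study says that "only pre-treatment images are needed to generate high-fidelity post-treatment image predictions". Section 3 gives the generator's "input data: enhanced CT/MRI images at the patient's baseline, real post-treatment enhanced CT/MRI images and clinical features", "with the treatment protocol (TACE embolic agent dose + target immune drug combination) as the generation conditions". The real post-treatment images are what generated images are compared with during training.

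On what enters the survival model, the protocol is not consistent. Section 3 says "Capture 256-dimensional semantic feature vectors from the generated virtual images" and fuses these with clinical variables. Main objective 3 in section 1 is to "predict the prognosis of patients based on real pre-treatment imaging images (CT/MRI/DSA) and virtual post-treatment images", and section 5 (innovation) says "Combine virtual and real pre-treatment images with other clinical information for accurate prognosis prediction".

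**The concern.** The project justification criticises existing models for resting on the patient's baseline status and offers generated post-treatment images as the advance. The natural model to beat is therefore one that uses the baseline scan directly, and it is not in the list. The contrast that carries the claim, virtual image against clinical variables only, changes two things at once: it brings image information into the model, and it passes that information through the generator. A gain could come wholly from the first.

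At stake is one conclusion, the incremental prognostic value of generation over the scan already in hand. The image-fidelity index, the blinded expert scoring, the comparison of response and disease control rates, and the contrast between virtual and real follow-up images still assess fidelity and substitution.

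**Working it through.** **1. The models set against the question.** Write X for clinical and treatment variables, B for the real pre-treatment scan, F for real follow-up images and V for the virtual image.

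| Model | Inputs | In the listed comparison? |
|---|---|---|
| (i) | X | yes |
| (ii) | X + F | yes |
| (iii) | X + V | yes; whether B is also included is not stated |
| (iv) | X + B | no |
| (v) | X + B + V | only if (iii) is meant to include B |

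At prediction time V = g(B, X, generator noise). Given B and X, the virtual image holds no further information about the individual patient. It can help only if training on real follow-up images lets the generator bring out scan signal that a direct image encoder misses. That contribution is C(v) − C(iv). The list offers C(iii) − C(i), which also contains the value of B. Model (ii) does not resolve this: F is later, observed information, so C(iii) against C(ii) tests substitution for follow-up, not what V adds to B.

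**2. Both readings of model (iii).** If it excludes B, the combination in main objective 3 is never compared with anything. If it includes B, it is (v), and its contrast with (i) adds B and V together. In both cases (iv) is absent.

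**3. Possible size.** The protocol states no sample size, event count or expected C-index difference for this comparison, so there is no figure to reproduce. All inputs below are assumptions.

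- Log hazard = 0.5·x + β·s, with x the clinical score and s the scan signal, both in SD units; β = 0, 0.3, 0.5, 0.7.
- s = √(1−e)·b + √e·u, where b is what a direct encoder extracts and u is surfaced only by the generator; e = 0, 0.25, 0.5.
- Virtual feature v = ρ·s + noise, with correlation ρ = 0.7 or 0.95 with s.
- Exponential survival, uniform censoring on 0 to 3 (about 66% events), n = 4000, Cox model fitted on half, Harrell's C on the other half, 10 replicates.

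C-index gains; ranges span the two values of ρ (for the listed contrast, also the values of e):

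| β | Listed: (iii) − (i) | (v) − (iv), e = 0 | e = 0.25 | e = 0.5 |
|---|---|---|---|---|
| 0 | 0.000 | 0.000 | 0.000 | 0.000 |
| 0.3 | 0.010–0.018 | 0.000 | 0.000–0.003 | 0.003–0.009 |
| 0.5 | 0.026–0.047 | 0.000 | 0.002–0.008 | 0.008–0.021 |
| 0.7 | 0.047–0.081 | 0.000 | 0.003–0.014 | 0.013–0.034 |

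C-indices at β = 0.7, ρ = 0.95:

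| e | (i) | (iii) | (iv) | (v) | (iii) − (i) | (v) − (iv) |
|---|---|---|---|---|---|---|
| 0 | 0.616 | 0.697 | 0.705 | 0.704 | 0.081 | 0.000 |
| 0.25 | 0.617 | 0.697 | 0.685 | 0.698 | 0.080 | 0.014 |
| 0.5 | 0.617 | 0.697 | 0.664 | 0.698 | 0.080 | 0.034 |

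Differences were taken before rounding, so the last digit can be off by one. The listed contrast stays the same while the generator's true contribution goes from nothing to 0.034. A repeat with other random numbers gave 0.085 / 0.080 / 0.084 for the listed contrast and 0.000 / 0.014 / 0.035 for the added value.

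**4. A second, simpler set-up.** Here there is no censoring, 4000 training and 2000 test patients, a clinical coefficient of 0.5, and a virtual feature equal to the scan feature plus noise (SD 0 or 0.5), so generation adds nothing by construction. The listed contrast showed gains of about 0.02, 0.06–0.08 and 0.10–0.13 for scan coefficients of 0.3, 0.6 and 0.9. Against the clinical plus scan model, the gain was 0.00 in all six settings.

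**The case against.** **The listed models fit the question of substitution.** The protocol presents generation largely as a stand-in for follow-up images that cannot be obtained. For that purpose clinical-only as floor, real follow-up as reference and virtual as substitute is coherent, and no objective formally states superiority over a baseline-scan model. This stands as far as it goes. But the protocol also sets its approach against models built on baseline status, and readers will take a gain over clinical-only as evidence for generation.

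**The list may not be exhaustive, and an analysis plan not shown could add a model.** It could. Main objective 3 already implies model (v), so perhaps only (iv) is new. But the protocol does spell out its comparison, and as written it does not support the attribution.

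**The three names in the list (baseline, benchmark, datum) may not be the same model.** The text, probably translated, does not settle this. Suppose the benchmark or datum model did include the scan: every model holding it would then also hold follow-up or virtual images, and clinical plus scan alone would still be missing.

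**The simulation is invented and its result is built in.** Its inputs are indeed assumed. It uses one scalar feature where the protocol describes a 256-dimensional Transformer pipeline, and the constancy of the listed contrast follows from how the virtual feature is defined. The simulation shows the direction and a plausible scale. The conclusion rests on the text.

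**Angiography.** Objective 3 includes DSA among the pre-treatment images, while the generator uses CT/MRI. This does not disturb the proposed contrast if (iv) and (v) share the same pre-treatment inputs.

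**Conclusion.** The concern holds and should be fixed. No model in the stated comparison isolates what the generative step adds to prognosis beyond the pre-treatment scan. This follows from the listed models and the generator's inputs and depends on no numerical assumption. Under the assumed values, an apparent C-index gain of about 0.01 to 0.08 over clinical-only can coexist with a true added value of zero, and of at most 0.034 even when half of the scan signal is accessible only through the generator. If the scan has no prognostic value, both are zero. The finding does not say that generation is useless, and it leaves the assessments of image fidelity and substitution untouched.

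**What to change.** In the comparative design of section 3:

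- Add (iv), clinical variables plus real pre-treatment images, with the same encoder, fusion architecture and tuning budget as the virtual-image model.
- Add (v), clinical variables plus real pre-treatment images plus virtual images, with the same clinical, treatment and pre-treatment image inputs as (iv).
- State whether the existing virtual-image model includes the pre-treatment scan, and align section 3 with main objective 3 and section 5. If it does include the scan, it is (v) and only (iv) is new.
- Base any claim that generation improves prognosis prediction on the paired difference in overall-survival C-index, (v) minus (iv), in the same test patients, with a 95% confidence interval from the 1000 bootstrap resamples already planned.
- Keep the clinical-only and real-follow-up models as references.

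The cost is one or two further models trained on images already collected and a few sentences of text, with no extra patients or data. The reported gain may turn out smaller.

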(3) The models are mostly constructed based on the baseline status of patients, ignoring the dynamic changes of tumor burden and immune landscape in the treatment cycle, which is difficult to guide treatment adjustment in real time and does not meet the needs of precision medicine. Although the traditional longitudinal prediction model can incorporate dynamic changes, it needs to systematically collect follow-up data for multiple visits. In the real world, patient follow-up is often irregular, and there are medical referrals and referrals in other places, resulting in a large number of missing or uneven longitudinal imaging data, and it is difficult to align the information obtained at different time points and different devices. In addition, such models wait for patients to respond to treatment, which has a prediction lag. The LILAC system (Learning-based Inference of Longitudinal imAge Changes) represents an important breakthrough in this direction, which uses a self-supervised time-series deep learning algorithm to analyze small changes in a series of MRI scans to achieve dynamic monitoring of disease progression. The proof-of-concept study showed that LILAC was significantly superior to the traditional method in the prediction of embryonic development time sequence and geriatric cognitive score. In pediatric glioma studies, the time-series deep learning model improved the F1-score of 1-year recurrence prediction by 58.5% by analyzing serial postoperative MRI images, and the prediction performance increased with the increase of historical scans (plateau after 3-6 scans). However, the clinical translation of longitudinal models faces fundamental difficulties: patients with advanced HCC are often unable to complete the full process of imaging follow-up due to disease progression or adverse reactions, resulting in a lack of high-quality time series data; Data heterogeneity is caused by differences in image acquisition protocols in different centers. Ethics and privacy concerns limit multi-center data sharing. Therefore, there is an urgent need to develop new prediction paradigms that do not rely on real post-treatment images. Breakthroughs in Generative Artificial Intelligence provide a revolutionary solution to this.

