## 2) Validity:

Overall survival (OS) is defined as the time from the start of chemotherapy combined with immunotherapy to the patient's death from any cause, measured in "months". For subjects who were still alive at the time of data analysis, OS was calculated based on the date on which the subjects were last known to be alive;

Progression-free survival (PFS): defined as the time from the start of chemotherapy combined with immunotherapy to the first disease progression or death from any cause.

To assess response to treatment in patients with intrahepatic lesions:

- a. Objective response rate (ORR): according to RECIST 1.1 criteria, objective response rate = (CR + PR / CR + PR + SD+PD); Participants with CR + PR efficacy should be retested 4 weeks after the first evaluation.
- b. Disease control rate (DCR): according to RECIST 1.1 criteria, lesion control rate = (CR + PR + SD/ CR + PR + SD + PD); Subjects with CR + PR + SD efficacy should be retested 4 weeks after the first evaluation.

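### The real-image benchmark sets no time limit on the follow-up scan; on the natural best-response reading it gains false discrimination, and the virtual model looks worse against it than it is

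*Protocol*

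**What the plan says.** The comparison is in the Protocol, section 3 (Research Methodology). Its three arms are a clinical-variable model, "benchmark model + real follow-up images", and the clinical model with the generated image. The main measure is the C-index for OS. The secondary measure is "12/24/36 months of time dependence on AUC to assess discriminant ability at a specific time point".

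The clock is set under the heading 2) Validity: "Overall survival (OS) is defined as the time from the start of chemotherapy combined with immunotherapy". Survival is therefore counted from the start of treatment, not from the date of any follow-up scan. No section gives a window, a last admissible date or a landmark for the real scans.

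Wherever the protocol identifies a post-treatment image, it is the best-response one:
- Section 1 (Research Objectives), main objective 2: response read from the virtual images is to be "compared with the best treatment response images after real treatment".
- Section 3: the generator is to "dynamically simulate the virtual follow-up images of the best response after treatment". The training paragraph then compares generated images with real follow-up images, the same term that names the benchmark arm.
- Section 5 (The innovation of the project): the model is to "generate imaging images of the best efficacy after virtual treatment".

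The background section on current status and challenges says that "patients with advanced HCC are often unable to complete the full process of imaging follow-up due to disease progression or adverse reactions".

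**The concern.** A best-response scan is a maximum over the scans a patient has had. A patient who dies at five months offers few candidates; one who lives three years offers many. Even if the images carried no prognostic information, the best of many would look better than the best of few. Survival time would then be part of its own predictor. The virtual image needs only pre-treatment images, so it cannot gain in this way, and the two arms are not compared on equal terms.

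At stake is the gap between the real-image and virtual-image models. That gap tells the reader what is lost by having no follow-up scan, which is the premise of the project. If part of it is false, a sound virtual model may be judged inferior. The gain of real images over clinical variables alone is overstated for the same reason.

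**Working it through.** The protocol gives no C-index, scan count or sample size on this point, so there is no figure of its own to reproduce. The check covers the mechanism first, then its size under stated assumptions.

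**1. Why the number of scans matters.** Write scan j of patient i as √ρ·uᵢ + √(1−ρ)·eᵢⱼ, with u and e standard normal and unrelated to survival. Here ρ is the within-patient correlation and larger values mean a better response. The expected best of k scans is √(1−ρ)·mₖ, with m₁ = 0, m₂ = 1/√π = 0.564 and m₃ = 3/(2√π) = 0.846. A patient with three scans therefore exceeds a patient with one by:
- ρ = 0.5: 0.707 × 0.846 = 0.60 SD
- ρ = 0.8: 0.447 × 0.846 = 0.38 SD

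This difference arises only from having lived long enough to be scanned three times. A time trend changes it. If lesions regrow by 0.25 SD per scan, the third scan is on average 2 × 0.25 = 0.5 SD worse than the first and is less often the best. Continued shrinkage does the opposite.

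**2. Size by simulation.** All inputs are assumptions:
- exponential OS with median 18 to 30 months and a clinical covariate with log HR 0.65 per SD (clinical C about 0.66 to 0.67);
- censoring uniform over 6 to 60 months;
- scans every 2 months until death or censoring, with the best of up to 3 or 6 used;
- images that are pure noise, so the true gain is zero;
- Cox models fitted on 1,500 patients and scored on another 1,500.

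False gain in OS C-index over the clinical model:

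| Time trend per scan | Correlation 0.8 | Correlation 0.5 |
|---|---|---|
| None | 0.000 to 0.007 | 0.002 to 0.020 |
| Regrowth 0.25 SD | 0.000 to 0.004 (both correlations together) | |
| Continued shrinkage 0.25 SD | 0.004 to 0.064 (both correlations together) | |

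With no trend and zero correlation between scans of the same patient, which is an extreme case, the range is 0.007 to 0.048. With no trend, the 12-month AUC gains 0.001 to 0.011 at correlation 0.8 and 0.004 to 0.030 at 0.5.

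**3. Does limiting the scan remove it?** Under noise with no trend, the first scan gives −0.001 to 0.000. Best response so far at a 4- or 6-month landmark, with survival counted from the landmark, also gives −0.001 to 0.000, or up to 0.003 if scanning stops at progression.

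A separate set of runs with the image as sole predictor (true C 0.50) shows that a window alone is not enough when several scans fall inside it. Best response within 6 months, with OS still counted from treatment start, gave 0.51 to 0.55. Moving the clock to the landmark brought it back to 0.49 to 0.51.

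**The case against.** The strongest reply is that the defect is conditional and belongs in a statistical analysis plan. The comparative-design sentence speaks only of real follow-up images, and the explicit mention of the real best-response image belongs to the response objective. It is correct that the protocol does not name the scan, and a reader who infers that the best-response scan is prescribed goes too far. But the protocol already fixes the comparison, the measure and the clock, and it uses the same term for the images matched to generated best-response images in training. Best response is the natural reading, and following the text on that reading produces the bias.

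Second, the bias works against the sponsor's own model. This stands. A reader might infer that the main claim for virtual images is inflated; the documents do not support that. The arm affected is a benchmark, and no test or margin for virtual versus real is stated.

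Third, the size depends on the time trend. This also stands. With quick regrowth the gain nearly vanishes, so a statement that the false part of the gap outweighs the honest part is not established.

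Fourth, the retest rule, "Subjects with CR + PR + SD efficacy should be retested 4 weeks after the first evaluation", might be read as proof that scan number grows with survival. It is not: it asks for one repeat assessment. The support comes from the background section's remark that progression and toxicity cut imaging short, and from the plain fact that scanning ends at death.

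Fifth, the time-origin wording is a separate matter. A uniform shift in start date leaves the C-index ranking unchanged, so it adds no weight here.

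**Conclusion.** The point holds in a limited form. The plan sets no limit on when the benchmark's real scan may be taken, counts OS from treatment start, and most naturally implies the best-response scan. On that reading the real-image arm gains discrimination that is not real. The direction holds unless response worsens quickly over time, in which case the effect shrinks to about zero.

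The size is unknown. Under the assumptions above it runs from nothing to about 0.02 in C-index with no trend, and to about 0.06 with continued shrinkage. Only comparisons that include the real-image arm are affected. It should be fixed, because the remedy needs no new data and has to be settled before modelling; it does not threaten the study's main result.

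**What to change.** For comparisons that include the real-image arm, state one of these before any model is fitted:
- **(a)** Use the first post-treatment scan within one fixed early window, and score all three models in the same patients.
- **(b)** Use best response so far up to one fixed landmark. Score all three models from that landmark in the same patients still at risk, and report how many are lost and why.

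Choose the window or landmark from scan dates only, without looking at outcomes. Keep the treatment-start clock and the full test sets for clinical-only versus virtual, and require no follow-up scan there.

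The cost is a smaller comparison set and, in (a), a real image less like the best-response virtual image. Under the assumed OS, a landmark loses 1 − 0.945 = 5.5% to 1 − 0.911 = 8.9% of patients at 2 months, and 1 − 0.848 = 15.2% to 1 − 0.766 = 23.4% at 6 months. If a further 10 to 30% have no scan by then (assumed), the totals are:
- 2 months: 1 − 0.945 × 0.90 = 15% to 1 − 0.911 × 0.70 = 36%
- 6 months: 1 − 0.848 × 0.90 = 24% to 1 − 0.766 × 0.70 = 46%

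The added loss may be smaller, because the exclusion criteria already remove patients with missing imaging data.

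Separately, the OS and PFS start event under 2) Validity does not match the study treatment in the selection criteria and in section 3 (TACE with targeted immunotherapy). Reconcile these passages and use one dated start event at all centres.
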